## ***The Women TAF-FTC Benchmark Study***

### **Safety and Pharmacokinetics of TAF-FTC Pre-exposure Prophylaxis in Kenyan Cisgender women**

#### **STUDY SUMMARY**

#### **PROTOCOL ABSTRACT/SUMMARY**

Pre-exposure prophylaxis (PrEP) using co-formulated emtricitabine (FTC) and tenofovir disoproxil fumarate (TDF) is a potent HIV prevention method for cis- and transgender men and gender women. Efficacy is highly dependent on adherence. Pivotal studies that combined clinical epidemiology and pharmacology defined thresholds for PrEP protection in cisgender men who have sex with men (MSM) that have been key to PrEP promotion and development of new PrEP agents. For African cisgender women at risk for HIV, a priority group due to disproportionately high incident HIV infections, variable adherence in PrEP clinical trials and limited pharmacokinetics data have resulted in lack of clarity about levels of PrEP use required for HIV protection. A new form of tenofovir, tenofovir alafenamide fumarate, co-formulated with emtricitabine (TAF-FTC) or Descovy® has recently been approved by the U.S. Food and Drug Administration for PrEP use in cisgender men and transgender women. However, Descovy® is not indicated in at risk cisgender women because its safety and effectiveness in this population has not been evaluated. Studies are now planned or ongoing in African cisgender women to evaluate TAF-FTC for PrEP. Tenofovir-diphosphate (TFV-DP) in dried blood spots was critical for interpreting Descovy® study outcomes in the DISCOVER trial, and will again be essential for the planned studies to evaluate the effectiveness of Descovy® for PrEP in cisgender women. Thus, clear knowledge of African cisgender women-specific adherence-concentration benchmark for TAF-FTC relationship is essential to define success of these studies. To date, no study has evaluated safety and directly observed expected TAF-FTC concentrations in African cisgender women with varying frequency of PrEP adherence. TAF efficiently achieves higher concentrations within lymphoid cells while attaining lower TFV concentration in plasma compared to TDF. This creates potential advantages of TAF for PrEP, as the higher TFV-DP in lymphoid cells may confer high activity, whereas the lower plasma TFV concentrations may improve markers of bone and renal changes compared with TDF. Although the clinical significance of these marker changes is unknown, it is thought that TAF may exhibit improved long-term safety compared with TDF. We will conduct an open-label, randomized, three-arm, directly observed dosing pharmacokinetics study of TAF-FTC PrEP in African cisgender women. The primary objectives are: **1) To assess the safety of TAF-FTC PrEP in cisgender women. 2) To define the cisgender women-specific expected blood concentrations and dose-proportionality for TFV-DP in DBS and PBMCs using directly observed TAF-FTC therapy at 2, 4, 7 doses per week. 3) To establish a model to predict adherence rate to TAF-FTC by level of TFV-DP in DBS for cisgender women.** HIV-uninfected non-pregnant cisgender women will be randomly assigned to 1 of 3 dosing frequencies of directly observed therapy (DOT) TAF-FTC PrEP: 2, 4, or 7 doses/week, to represent poor, modest, and perfect adherence, respectively. The study will enroll up to 54 18-30 years old HIV uninfected cisgender women at low risk of HIV at Thika site in Kenya. The proposed study will be the first to define TAF-PrEP adherence-blood concentration thresholds for African cisgender women, a priority population for HIV prevention. The findings will guide accurate interpretation of safety, adherence, and efficacy of planned or ongoing HIV prevention trials in African cisgender women.

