### Justification for non-daily dosing of PrEP groups:

In this study we propose to randomize cisgender women to non-daily dosing of PrEP (2, or 4 doses per week). The non-daily dosing is needed to investigate and demonstrate dose proportionality of TFV and TFV-DP concentrations. The adherence-concentration thresholds derived from this dosing frequency will help guide appropriate interpretation of adherence to TAF-based PrEP in clinical studies and implementation programs of PrEP. To minimize the risk of HIV infection in the non-daily dosing groups, as detailed in the eligibility section, only non-pregnant cisgender women at low HIV risk based on Kenya

guidelines will be enrolled and participants will receive a full package of HIV prevention, including risk reduction counseling, condoms and STI treatment at each visit. We will also perform monthly HIV testing. We will closely monitor the frequency of adverse events, including emergent HIV seroconversion (expected to be very rare) between groups.

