## 7.3 Data Analysis

### 7.3.1 Primary outcomes

**Primary outcome 1:** The goal is to describe the frequency of adverse events, including emergent HIV infection during the study period. We will conduct a descriptive analysis for meeting PrEP157 eligibility among participants. The distribution of demographics and graded adverse events will characterize by overall and study arms and proportions will be compared between study arms using chi-square statistics.

**Primary outcome 2:** The goal is to quantify the effect of dose on steady state TFV-DP in DBS and PBMC based on an incomplete block design.  $C_{ss}$  (drug concentration at steady state) will likely require a normalizing log transform, such that geometric means and CIs will be reported. Dose proportionality will be assessed using the power model (on the natural log scale)  $\ln(Y_{ijk}) = \mu + S_i + P_j + \beta \log(D_k) + \varepsilon_{ijk}$  (Eqn. 1). Where  $Y_{ijk}$  is the response,  $C_{ss}$ , for the  $k$ th dose ( $k=2, 4, 7$  doses/week),  $j$ th period ( $j=1,2$ ),  $i$ th subject ( $i=1, \dots, 45$ );  $\mu$  is the overall mean,  $S_i$  is a random subject effect,  $P_j$  is the period effect and  $\varepsilon_{ijk}$  is random error. Dose proportionality dictates that  $\beta=1$  for dose-dependent parameters and we will assume dose proportionality if the 90% CI is contained within the limits (0.8, 1.25). The SAS mixed procedure will be utilized for model (Eqn 1), again assuming a random subject effect. Although we do not anticipate a period effect, our design allows us to test this effect. For the primary analysis, we assume no effect of 'non-daily dosing' regimens; although this will be examined in a secondary analysis. If dose proportionality is not shown, we will examine proportionality separately for each of the "non-daily dosing" dosing regimens. If dose proportionality is still not demonstrated when adherence regimens are examined separately we will consider dose as a categorical predictor.

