In addition to the power model, we will utilize nonlinear mixed effects models using PK software (NONMEN and/or ADAPT-5) to model drug concentration over time on drug. For this analysis, all available drug concentration samples will be utilized, thereby accounting for missed doses due to protocol deviations. Change in objective function and/or AIC will be used to compare models. This approach will be used to further probe dose proportionality and the final model(s) will be used as a basis for simulation studies.

**Primary outcome 3:** The goal is to identify TFV-DP cut points associated with adherence levels. For the primary analyses, we will attempt to discriminate adherence for 2, 4 and 7 dosing based upon TFV-DP. As above, we will combine the "non-daily dosing" regimens. Linear mixed models with random intercepts, 25th percentiles, and receiver operating characteristics curves will be used to generate predicted concentration thresholds for varying dosing frequency (ranging from 1 to 7 doses/week) for each matrix-analyte pair. Analyses will be adjusted for age, contraception use, study arm, BMI, eGFR, and hematocrit.

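### Primary outcome 3: the instruction to combine the non-daily regimens (here the 2- and 4-dose arms) conflicts with the three-level goal before it and the 1-to-7-dose thresholds after it

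*Combined protocol and SAP*

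**What the plan says.** Section 7.3.1, primary outcome 3, seeks TFV-DP cut points that mark adherence levels. Three consecutive instructions matter. The first two, the goal and the pooling rule, run together: "we will attempt to discriminate adherence for 2, 4 and 7 dosing based upon TFV-DP. As above, we will combine the" non-daily dosing regimens. The third is the output: mixed models, 25th percentiles and ROC curves are to give concentration thresholds for frequencies from 1 to 7 doses a week.

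The term non-daily is fixed elsewhere. The justification in section 2.5 reads "we propose to randomize cisgender women to non-daily dosing of PrEP (2, or 4 doses per week", and sections 8.4 and 8.5 gloss it the same way. The abstract gives the arms their meaning: "2, 4, or 7 doses/week, to represent poor, modest, and perfect adherence, respectively".

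The words referring back in the pooling rule lead to primary outcome 2, where the text runs "For the primary analysis, we assume no effect of" non-daily dosing regimens. In that power model dose stays in as 2, 4 or 7. If proportionality fails, the non-daily regimens are examined separately, and after that dose becomes categorical.

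**The concern.** A classification rule needs its classes defined. The goal sentence asks for three, and the pooling sentence read at face value leaves two. Two analysts working from this paragraph could deliver different primary results: one with a single daily versus non-daily cut, the other with cuts at both 2 versus 4 and 4 versus 7.

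The trial's main product is a set of adherence benchmarks for reading drug levels in other TAF-FTC studies. The boundary between poor and moderate adherence is one of the distinctions those readers would look for. A percentile or ROC threshold from a merged class would describe neither regimen. If the classes are settled only after the concentrations are known, the choice is also open to being made with the data in view.

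**Working it through.** **Step 1: what can be combined?** Sections 2.5 and 5.2.1 give each arm one weekday pattern: Monday and Tuesday for 2 doses; Monday, Tuesday, Thursday and Friday for 4. Section 5.2.1 lets the days be changed before the study starts but adds no second pattern within an arm. Pooling patterns within one weekly frequency would therefore have nothing to act on, and only the 2- and 4-dose arms are left to pool. Secondary outcome 1 in section 7.3.2 uses the term in the same way: its reduced model sets non-daily dosing against 100% dosing.

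**Step 2: the classes.** Section 7.5 allocates 18/18/18. Pooling gives 18 + 18 = 36 non-daily against 18 daily, hence one boundary and none inside the pooled class.

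**Step 3: the other places that bear on it.**

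| Place | 2- and 4-dose arms |
|---|---|
| 7.2, Aim 1 | reported by dose |
| 7.3.1, primary outcome 2 | distinct (dose 2, 4, 7; categorical fallback) |
| 7.3.1, primary outcome 3, goal | distinct |
| 7.3.1, primary outcome 3, pooling rule | combined |
| 7.3.1, primary outcome 3, output | distinct (1 to 7 doses) |
| 7.3.2, secondary outcome 1 | saturated model distinct; reduced model combined |

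Among the primary-analysis statements, the pooling rule is the one out of line.

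**Step 4: illustration of the consequence.** The plan states no figure for this analysis, so there is none to reproduce. Inputs from section 7.4: daily-dosing mean 2381 and SD 601, so CV = 601/2381 = 0.252. Assumptions that are not in the plan: means proportional to weekly doses, log-normal values, the same CV in every arm, and a 25th percentile reported for the merged class.

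- Log-scale SD: σ = √ln(1 + 0.2524²) = 0.249.
- Daily median: 2381/√(1 + 0.2524²) = 2309. Times 2/7 and 4/7: 660 and 1319.
- 25th percentile = median × exp(−0.6745σ): **558** (2 doses), **1116** (4 doses), **1952** (7 doses).
- Merged 25th percentile: solve ½Φ(ln(x/660)/σ) + ½Φ(ln(x/1319)/σ) = 0.25, giving x ≈ **659**. That is 1 − 659/1116 = 41% below the 4-dose value and practically the 2-dose median, so about half of women on 2 doses would lie above it.
- AUC = Φ(ln(ratio)/(σ√2)). For 2 versus 4: Φ(0.693/0.351) = **0.98**. For 4 versus 7: Φ(0.560/0.351) = **0.94**.
- Accuracy at the log-midpoint, 2 versus 4: Φ(0.693/(2 × 0.249)) = 92%.

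At an assumed CV of 40% (σ = 0.385), the merged 25th percentile is 613, which is 37% below the 4-dose value of 974. The AUCs are 0.90 (2 versus 4) and 0.85 (4 versus 7), and the 2-versus-4 accuracy is 82%.

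Under these assumptions the boundary that pooling gives up is easier to draw than the one it keeps, simply because 4/2 exceeds 7/4. Feasibility is therefore no reason to pool.

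**The case against.** The best defence is that the pooling sentence does not mean what it appears to mean. It refers back to primary outcome 2, where assuming no effect of the non-daily regimens goes together with a model that still holds dose at 2, 4 and 7. On that reading, combining means fitting the arms in one dose model without a separate regimen term, and no merging of arms is defined anywhere. The very next sentence promises thresholds indexed by dosing frequency, which a two-class merge could not supply. The sentence may be carried over from another design: primary outcome 2 also mentions an incomplete block design, two periods and 45 subjects, none of which fits 54 women in three parallel arms.

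Most of this stands, and it limits the claim. A reader might infer that the trial cannot separate poor from moderate adherence, or that the distinction survives only as a secondary, hypothesis-generating item. The documents support neither. The arms are randomised and sampled separately, and Aim 1, the power model and the 1-to-7 thresholds all keep them distinct. The 2-versus-4 example in secondary outcome 1 uses the ratio of TFV-DP to FTC-TP, which is a different predictor and not a demoted form of the TFV-DP cut point.

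The defence does not remove the conflict. The regression reading explains the mixed model but does not tell an analyst what to do in the percentile and ROC steps, where combining regimens naturally means combining classes.

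**Conclusion.** The point holds as a contradiction inside a primary outcome. The pooling instruction conflicts with the sentences on either side of it, and the plan does not say which governs the percentile and ROC analyses. Applied literally there, it gives two classes (36 versus 18) and no primary cut point between 2 and 4 doses a week. This rests on the text alone.

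The figures (merged 25th percentile about 659 against 558 and 1116; AUC about 0.98, or 0.90 at CV 40%) only show the scale. They depend on dose proportionality, which primary outcome 2 is there to test; on a common CV, whereas section 7.4 gives variability for daily dosing only; and on a merged-class percentile being reported, which the plan does not expressly promise. The collected data are unaffected.

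**What to change.** In section 7.3.1, primary outcome 3:

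- Delete the sentence that combines the non-daily regimens.
- State three ordered classes: 2, 4 and 7 doses a week.
- Specify 25th percentiles for each arm and two TFV-DP cut points, 2 versus 4 and 4 versus 7.
- If a daily versus non-daily cut is wanted, label it as an additional pooled summary.

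The cost is a wording change, with no extra participants, samples or visits. It should be made before the concentration data are analysed, so that the classes are fixed in advance.

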## 2.3 Primary Objectives

- 1) To describe the safety of TAF-FTC-based PrEP in HIV-uninfected cisgender women.
- 2) To define the cisgender women-specific expected blood concentrations and dose-proportionality for TFV-DP in DBS and PBMCs in cisgender women using directly observed TAF-FTC therapy at 2, 4, 7 doses per week.

- 3) To establish a model to predict adherence rate to TAF-FTC by level of TFV-DP in DBS for cisgender women.

[figure not shown]

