### **5.2.1 Dosing schedule and assessment of compliance**

The design of the study is guided by the ~17-day half-life of TFV-DP in DBS, and includes 10 weeks of dosing to achieve approximately 90% of steady-state, weekly sampling at convenience times (i.e., rather than troughs), and three dosing groups (2, 4, and 7 doses per week) to demonstrate dose-proportionality. All cisgender women will have 10 weeks of DOT PrEP to establish steady state in DBS and WB. We have chosen a dosing frequency scheme for non-daily doses to directly replicate the STRAND DOT study schedule based on the ~17-day half-life of TFV-DP in DBS: The 2 doses per week will be taken on Monday and Tuesday, and the 4 doses per week on Monday, Tuesday, Thursday, and Friday. This schedule will permit simultaneous evaluation of concentrations derived from intermittent and day-by-day dosing. The operationalization of specific days for dose taking can be adjusted prior to study start while maintaining the randomized adherence patterns (frequency of dosing taking) to permit efficient study operations and to minimize the burden on study participants. This is possible due to the long half-life of TFV-DP and planned sampling at steady state. Therefore, any chosen days would be appropriate.

All doses will be witnessed, as described above, in person by a study personnel in either a private room at the Thika clinic or at another predetermined location to maximize convenience for the participant. On dosing visits, the participant will take the dose by mouth and study personnel will ensure the tablet is swallowed by asking the participant to show that their mouth is empty. Flexible clinic scheduling will be available to promote high rates of follow-up and compliance and to minimize participants' burden. Where dosing cannot be witnessed in person, dosing will be witnessed over video via WhatsApp, Zoom, FaceTime, Skype, or other video-streaming device that is agreed upon by the participant and study

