### 7.3.2 Secondary outcomes

1. Examine models to predict non-daily adherence based on TFV/FTC and FTC-TP/TFV-DP in DBS.

We assume the modeling approaches of Aim-1. We will first consider a saturated model allowing a separate mean for each dose/adherence group. The results will then be compared to a reduced model with a class variable indicating non-daily dosing groups" or 100% dosing (that is, the effect of "non-daily dosing" adherence does not differ by dose groups). Drug concentration predictors of "non-daily dosing" will focus on TFV-DP in relationship to other drug moieties such as FTC-TP and FTC and TFV. For instance, the ratio of TFV-DP to FTC-TP may be used as a predictor of "2" versus "4" dosing per week. A proportional odds logistic approach which allows for an ordinal outcome and extensions which control for correlations between repeated measurements on a subject will be utilized in SAS or R statistical software. In addition, we will employ PK models (see Aim-1) to simulate TFV-DP to FTC-TP ratios for other dose regimens and estimate cut points for predicting non-daily dosing patterns.

2. Examine relationships among drug concentrations in plasma, RBC, DBS, and PBMC.

We will use mixed and non-linear mixed effects models to determine if concentrations in various matrices are related.

3. Evaluate the influence of demographics, biological on drug concentrations.

Kruskal-Wallis parametric test will be used to compare demographics and key study variables (e.g., age, pregnancy, HCT, contraception use, study arm, BMI, eGFR). Non-linear mixed effects models also will be used to probe covariate effects on PK. Secondary analyses are considered hypothesis generating and will not correct for multiple comparisons.

4. Compare drug concentrations in DBS from fingerstick versus transferring blood from blood tubes.

Since these are paired DBS samples, we will compute the ratio of TFV-DP in the two samples and a mixed model on the natural log of the ratio will be utilized to determine if CI is within 0.8 and 1.25, indicating equivalence. Bland-Altman analyses will also be evaluated.

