#### 7.4 Sample Size Considerations

The overall sample size was chosen to have up to 18 cisgender women in each relevant group (overall, n=54 non-pregnant cisgender women) sufficient to provide precise information on drug concentrations and to balance feasibility, efficiency, and provide robust TAF/FTC data in DBS for cisgender women. The sample size for drug concentration parameters is based on ensuring precision in the estimates to accurately describe the concentration kinetics of TAF/FTC in non-pregnant cisgender women and is consistent with multiple DOT PrEP studies done in US populations. The precision desired is a mean TFV-DP in DBS at steady state within  $\pm 15\%$  of the true population mean. The mean ( $\pm$  standard deviation) TFV-DP at steady-state in HIV-uninfected US cisgender men and cisgender women following directly observed doses of 25 mg TAF/200mg FTC once daily for 12 weeks was  $2381 \pm 601$  fmol/punches [coefficient of variation (CV) of 25%] (*Anderson et al*). Based on this variability and assuming average TFV-DP results are normally distributed, to be 90% confident that the DBS TFV-DP sample mean is within 15% of the true mean, a sample size of 15 participants is required for non-pregnant cisgender women with conservative assumptions. With the planned enrollment of 18 cisgender women per group for this study, even a 10% non-completion rate at 8 weeks of DOT therapy, we provide ample data to estimate steady-state means to within 10% in cisgender women.

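### Primary outcome 3 plans no internal validation or interval method for its ROC-selected adherence cut points, and does not say how repeat samples per woman enter the ROC and percentile steps

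*Combined protocol and SAP*

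**What the plan says.** Section 2.3 makes prediction a primary objective: "To establish a model to predict adherence rate to TAF-FTC by level of TFV-DP in DBS". Section 7.3.1 states the aim of Primary outcome 3 as follows: "The goal is to identify TFV-DP cut points associated with adherence levels". The levels to be told apart are those of the three arms: 2, 4 and 7 doses per week.

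Three methods appear in one sentence. The first is "Linear mixed models with random intercepts". The second is the use of 25th percentiles. On the third, the plan says that "receiver operating characteristics curves will be used to generate predicted concentration thresholds". The sentence wants these thresholds at dosing frequencies from 1 to 7 per week, and for every matrix-analyte pair.

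Two provisions deal with repeat samples. One is the random intercept, which belongs to the linear mixed model. The other is in Section 7.3.2, for the secondary proportional odds model: "extensions which control for correlations between repeated measurements on a subject will be utilized in SAS or R statistical software". Neither is stated for the ROC curves or the percentiles.

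Section 7.4 plans up to 18 women per arm, 54 in all. Section 5.2.1 and Table 2 have blood taken weekly during dosing, so each woman supplies many DBS values. No section names a hold-out set, cross-validation, a bootstrap, a validation cohort, or an interval method for the cut points. The simulation studies in Section 7.3.1 rest on the population PK model and are not described as a check of the cut points.

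**The concern.** Sections 1.1.3 and 1.2 say the results will be used to interpret drug levels and DBS testing in other TAF-FTC trials in African women. A threshold used in that way needs an honest statement of how well it classifies and how precisely it is known.

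Two separate problems arise:

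- **Optimism.** An ROC search picks the cut that separates these particular women best. Accuracy measured in the same women is biased upward, and the bias is larger when groups are small and overlap.
- **Clustering.** Several samples from one woman are correlated. If they entered the ROC or percentile step as independent values, the intervals would be too narrow.

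The first applies to any ROC-selected cut. The second depends on a choice that the plan leaves open.

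**Working it through.** **The plan's own figure.** There is none for cut-point accuracy. The only sample size figure, 15 per group in Section 7.4, is for the precision of a mean. With its stated inputs, n = (1.645 × 0.25 / 0.15)² = 7.5, so 8 (10 with the t distribution). The 15 therefore rests on conservative assumptions that are not spelled out. It errs on the safe side and has no bearing on this point.

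**Inputs from the protocol.** 18 women per arm, so 36 per pairwise contrast. CV 25% (601/2381 = 25.2%), from daily dosing in US men and women. Doses 2, 4 and 7 per week.

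**Assumptions.** Log-normal TFV-DP; means proportional to dose (ratios 1.75 for 7 v 4, 2.0 for 4 v 2, 3.5 for 7 v 2); the same CV in every arm; cut chosen by the highest Youden index (sensitivity + specificity − 1). For repeat samples, three per woman and an ICC of 0.5 to 0.9.

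**Step 1: optimism of ROC cuts.** Simulation with 4,000 datasets per setting. Apparent = Youden index in the data that chose the cut. True = Youden index of that cut under the generating model. One sample per woman, CV 25%:

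| Contrast | Apparent | True |
|---|---|---|
| 4 v 7 | 0.81 | 0.71 |
| 2 v 4 | 0.90 | 0.81 |
| 2 v 7 | 0.998 | 0.98 |

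As a check on scale for 4 v 7, the log-scale SD is √ln(1 + 0.25²) = 0.246 and the separation is ln 1.75 = 0.560. The best attainable Youden index is 2Φ(0.560 / (2 × 0.246)) − 1 = 0.74. The average apparent value of 0.81 is above what any cut could achieve.

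For 4 v 7 with three samples per woman, the gap shrinks to about 0.79 v 0.72. With one sample per woman and a CV of 35% (assumed), it is 0.68 v 0.56.

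**Step 2: instability of the cut.** For 4 v 7, one sample per woman, CV 25%, the 5th to 95th percentile range of the chosen cut is about 1.12 to 1.51 times the 4-dose geometric mean. That is 1.51 / 1.12 = 1.35-fold, while the two arms differ only 1.75-fold.

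**Step 3: the other two methods.** With the 25th percentile of the 7-dose arm as the cut, apparent and true values agree (0.667 v 0.666). A model-type cut midway between the two arms' log means gives 0.754 v 0.738. Nearly all the optimism therefore belongs to the ROC search.

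**Step 4: intervals if samples were pooled.** Design effect = 1 + (m − 1) × ICC. With m = 3 this is 2.0 at ICC 0.5 and 2.8 at ICC 0.9. Coverage of a nominal 95% interval = 2Φ(1.96 / √deff) − 1, which is 83% and 76%. This formula is for a mean. A direct simulation of pooled AUC intervals at CV 25% gave 66% to 82%.

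**Step 5: how much the remedy recovers.** An optimism bootstrap by woman for 4 v 7, on balanced accuracy (= (Youden + 1) / 2), gave:

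- One sample per woman: apparent 0.909, corrected 0.879, true 0.855. It removes 0.030 of 0.054, about half.
- Three samples, ICC 0.7: 0.890, 0.868, 0.860. It removes 0.022 of 0.030.

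**The case against.** The strongest reply is that the plan does not rest on ROC alone. Thresholds are wanted for 1 to 7 doses per week but only 2, 4 and 7 are given, so those for 1, 3, 5 and 6 must come from a model. The model named has random intercepts, which handle repeats by woman. This stands, and it limits the point to cuts that ROC selects.

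A reader might infer that every planned threshold is optimistic. Step 3 shows otherwise: a 25th percentile is a fixed quantile and is not tuned to accuracy.

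A reader might also infer that the plan pools repeat samples as independent, or will publish apparent sensitivity and specificity uncorrected. It says neither. ROC on one steady-state value per woman would fit the text equally well, and no accuracy measures are named. Section 7.3.2 shows that the authors know about within-woman correlation. The interval result in Step 4 is therefore conditional.

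The size also depends on the contrast: 4 v 7 is the closest pair, and for 2 v 7 the optimism is negligible. The figures in Steps 1 and 4 belong to different scenarios (one sample against three pooled samples) and should not be added together.

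What remains is that a primary outcome yields cut points for use elsewhere, and the plan gives no way to estimate the accuracy or the uncertainty of those chosen by ROC.

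**Conclusion.** The point holds in this limited form and is a cheap improvement. ROC-selected cuts have no planned internal validation. At the plan's CV of 25%, the apparent Youden index for adjacent dose groups would overstate the true one by about 0.09 to 0.10 with one sample per woman, and for 4 v 7 by about 0.07 with three. For 2 v 7 the excess is under 0.02.

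The plan also names no interval method for any threshold, and the handling of repeats in the ROC and percentile steps is unspecified. Pooling would bring coverage down to roughly 83% to 76%, but the documents do not say that pooling is intended.

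These sizes rest on dose-proportional means, log-normality, a common CV and a Youden-type cut. The ICC and the number of samples per woman are assumed, because the documents give neither. Optimism grows if the CV in Kenyan women, or in the non-daily arms, is above 25%.

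**What to change.** In Section 7.3.1, Primary outcome 3:

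1. State which steady-state visits enter the ROC and percentile analyses, and whether each woman contributes one value or several.
2. Derive the confidence interval of every threshold by a bootstrap that resamples whole women within arm.
3. For ROC cuts, name the selection criterion and repeat the full cut-point search inside each bootstrap resample or leave-one-woman-out fold.
4. Report optimism-corrected sensitivity, specificity and AUC beside the apparent values. Note that internal correction removes only part of the optimism at this sample size (about half in the one-sample case above), so confirmation in other women is still needed.

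The cost is extra analysis code and less favourable reported accuracy. No further participants, visits or samples are needed.
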